## 6.3 Exclusion criteria

Women who have been pregnant for more than 16 weeks at baseline visit will be excluded from the study.

## 6.4 Withdrawal criteria

Patients may withdraw at will at any time, for any reason.

## 6.5 Rationale for study population

The Diabetes Pregnancy Registry is a non-interventional epidemiological study where data are collected on standard routine procedures. The results and observations from the registry will, hence, be more broadly applicable to the real-world population of pregnant women with DM, and their infants than study populations enrolled in a typical randomised controlled trial.

Only women with either T1DM or T2DM who are treated with Levemir® or other injectable antidiabetic treatment regimens and who have not changed basal insulin or other injectable antidiabetic product (for those not treated with insulin) 4 weeks prior to and following conception will be included. During the pregnancy the women attend regular visits to specialist clinics for the treatment of their DM and therefore, it is optimal to contact experienced clinics with a high number of potential candidates.

Gestational DM has been excluded because the women may not develop the disease until late in pregnancy, where the organogenesis is finalized and thereby the risk of malformation significantly reduced. Furthermore, at least a fraction of these may control the gestational DM by diet alone.

## 7 Study schedule

Timelines may be adjusted during the course of the present non-interventional study.

Planned date for first patient first visit: Q3 2013

Estimated completion of the last patient (last patient last visit, LPLV): Q2 2020

The end of the non-interventional study is defined as LPLV

Planned completion of non-interventional study report: Study progress reports will be submitted to the participating clinics and the European Medicines Agency (EMA) on an annual basis. This study is subject to registration no later than 21 days after enrolment of the first study participant according to a Novo Nordisk A/S requirement on non-interventional study disclosure. Only the main study site per country will be disclosed via facility name, city and country on the study registration.

Note: Study registration is regarded as the publication of an internationally-agreed set of information about the design, conduct and administration of clinical trials. These details are published on a publicly-accessible website managed by a registry conforming to World Health Organization (WHO) standards (e.g. [www.clinicaltrials.gov](http://www.clinicaltrials.gov) and [www.encepp.eu](http://www.encepp.eu)).

All physicians will be notified by Novo Nordisk A/S immediately when the recruitment period comes to an end, after which no patients must be enrolled.

## 8 Methods and assessments

The Diabetes Pregnancy Registry will include maternal and paediatric assessments as per standard practise. There are differences in the endpoints covering the gestation period, the delivery, the pregnancy outcomes, the postpartum visit and the follow-up in the infants. The variables on the study forms will depend on these different endpoints.

All parameters which will be collected in this registry are defined in accordance with normal clinical practice. Relevant registry forms for the baseline visit including potential confounders, standard routine visits, delivery visit, the postpartum visit and the follow-up of the infants are developed together with some of the study sites participating in the registry.

Signed informed consent must be obtained prior to any data entry into the registry.

After the Informed Consent Form has been signed, patients will be allocated an ID number, which will remain unchanged throughout the study. The physician will assign each enrolled patient with a unique 6 digit patient number. The patient number is composed of 3 digits unique for each study site followed by 3 consecutive digits for each enrolled patient on the study site. If an eligible woman is included in the Diabetes Pregnancy Registry more than once, she will be allocated a new patient ID number for each pregnancy that may occur during the recruitment period. The infant(s) of the patient will be allocated the same ID number as its mother followed by a "Xn" at the end of the 6 digit patient number (n=1, 2, 3 and so forth for each child).

Patients enrolled in the study will be provided with contact address and telephone number of the physician site and/or staff.

In case a patient is withdrawn from the study the physician will ensure that the primary reason for discontinuation will be specified in the eCRF.

This section describes the general study procedures applicable for all patients. Visit and contact specific procedures are described in sub-sections below.

### 8.1 Visit procedures

An eCRF should be completed for all patients.

The standard, routine treatment of the individual patients enrolled into the registry should not be influenced by or interfered with following recruitment. Therefore the data collected is only what is collected as part of standard routine and missing data is expected. All data collected at the visits is data from standard routine procedure visits and the frequency of these visits is determined by the individual study site. The delivery information and the information collected at 1 month and at 1

year follow-up are not necessarily standard procedures, but the data collected will be part of standard routine assessments.

The physician must keep a patient enrolment log throughout the enrolment period.

### **8.1.1 Baseline visit**

Signed informed consent must be obtained before any data recording is performed for the purpose of this non-interventional study.

The following will be performed at the baseline visit which will occur as soon as the woman has discovered her pregnancy through a positive pregnancy test:

- Check of eligibility against inclusion criteria (section [6.2](#))
- Check whether the patient has previously participated in the registry (if yes, please state previous patient ID number)
- Demographics (section [8.3.1](#))
- Obstetric history (section [8.3.2](#))
- Maternal medical history (section [8.3.3](#))
- Maternal diabetes history (section [8.3.3](#))
- Current insulin and/or injectable antidiabetic treatment and/or OAD use (section [8.3.3](#))
- Concomitant illnesses (section [8.3.4](#))
- Concomitant medication (section [8.3.4](#))
- Anthropometric measurements (section [8.3.5](#))
- Vital signs (section [8.3.6](#))
- Current pregnancy (section [8.3.7](#))
- HbA1c level assessed according to standard routine at local laboratories (HbA1c level measured  $\leq$  16 weeks prior to baseline visit is acceptable as baseline visit data)

### **8.1.2 Standard routine visits**

The standard routine practice covers all visits to the clinic after the baseline visit. These visits may differ in frequency between the study sites. Preferably data from one standard routine visit per month should be entered into the eCRF irrespective of the number of visits performed. The following information should, however, be recorded at each standard routine visit, if available:

- Weight measurement (section [8.3.5](#))
- HbA1c level assessed according to standard routine at local laboratories
- Current insulin and/or injectable antidiabetic treatment and/or OAD use, only required if the type of insulin or product has changed since last visit (section [8.3.3](#))
- Change in concomitant medication (section [8.3.4](#))

- Vital signs (section [8.3.6](#))
- Major hypoglycaemic events since last visit (section [8.3.8](#))
- Congenital malformations in the foetus
- ADRs, SAEs, and all major hypoglycaemic episodes and pre-eclampsia since last visit (section [9](#))

### **8.1.3 Delivery**

Relevant information during labour and delivery and neonatal assessment will be documented in the eCRF.

During labour and delivery, the use of insulin and glucose will be according to local practice.

The following will be recorded in the eCRF:

#### **8.1.3.1 Mother/foetus**

- Early or late foetal death including spontaneous or induced abortion must be reported in the eCRF (section [8.3.12](#)) and as SAEs (section [9.1](#))
- Insulin and/or injectable antidiabetic treatment and/or OAD use during delivery, only if the type of insulin or product has changed since last visit (section [8.3.3](#))
- Change in concomitant medication (section [8.3.4](#))
- ADRs, SAEs, major hypoglycaemic episodes and pre-eclampsia since the last visit (section [9](#))
- Delivery information (section [8.3.10](#))
- HbA1c level assessed according to standard routine at local laboratories

#### **8.1.3.2 Neonate**

Details on pregnancy outcome/neonatal assessment will be entered in the eCRF (section [8.3.11](#))

If the infant has any congenital anomaly/birth defect observed at examination this must be reported, recorded and followed up as a SAE according to section [9.1](#) and [9.2](#).

If the neonate has experienced any ADRs or SAEs, these should be reported.

#### **8.1.4 Post partum visit**

The postpartum visit will be a 1 month follow-up data collection of the infants to the women with an allowed visit window of +1 month. The follow-up will be performed as a questionnaire sent to the women and will be followed up with a telephone interview of the women. The date of visit to be entered in the eCRF should be the date where the body measurements were performed. It is not

mandatory to collect the completed questionnaires. The following information will be asked in the questionnaire:

- Height at the age of 1 month (approximately)
- Weight at the age of 1 month (approximately)
- Neonatal death of the infant (y/n)
- Congenital malformations (minor/major) not detected at delivery
- Duration of exclusive lactation and/or duration of partial lactation (section [8.3.13](#))
- If the neonate has experienced any AEs, only ADRs and SAEs should be reported in the eCRF

### **8.1.5 End of study visit**

The end of study visit will be a 1 year follow-up data collection of the infants to the women with an allowed visit window of +4 months. The follow-up will be performed as a questionnaire sent to the women with infants and will be followed up with a telephone interview of the women with infants. The following information will be asked in the questionnaire:

- Height at the age of 1 year (approximately)
- Weight at the age of 1 year (approximately)
- Duration of exclusive lactation and/or duration of partial lactation (section [8.3.13](#))
- Diabetes in the infants (y/n)
- Changes (progression/regression) of major congenital malformations
- If the infant has experienced any AEs, only ADRs and SAEs should be reported in the eCRF

## **8.2 Assessments for safety**

All ADRs and SAEs in pregnant women treated with any injectable antidiabetic treatment regimens, as well as in their off-spring until 1 year of age, should be reported. In addition, pre-eclampsia and major hypoglycaemic events in the pregnant women should be reported regardless of causal relationship and seriousness criteria. Please see section [9](#) for definitions and further detail.

If any additional safety reporting is required by local laws and/or Independent Ethics Committees (IECs)/Institutional Review Boards (IRBs), these should be complied with.

The physician will ask the pregnant woman participating during each visit if she has encountered any AEs or if she has experienced any hospitalisations or other SAEs. This may be done by posing a simple question such as “have you experienced any problems since the last visit/contact?” All ADRs and SAEs according to section [9](#) will be recorded in the eCRF.

All safety data collected regarding Levemir® treatment and other Novo Nordisk A/S products for pregnant women will be reviewed periodically and reported in the PSURs to EMA.

### **8.3 Other assessments**

#### **8.3.1 Demographics**

The following maternal information will be recorded at baseline visit:

- Date of birth
- Race
- Socioeconomic status (education, occupation)
- Recreational drug use
  - Tobacco (y/n, how much/day)
  - Alcohol (y/n, how much/day)
  - Other (y/n, how much/day)

#### **8.3.2 Obstetric history**

The following will be recorded at baseline visit:

- Previous pregnancies and outcome:
  - Number of previous pregnancies
  - Number of previous live birth
  - Previous pregnancy complications (y/n)
    - Pre-eclampsia
    - Caesarean section(s)
    - Perinatal death(s)
    - Preterm delivery(ies)
    - Spontaneous abortion(s)
    - Malformations (major/minor, by organ)

#### **8.3.3 Maternal medical history**

The following will be recorded at baseline visit:

- Medical history:
  - Hypertension (y/n)
  - Epilepsy (y/n)
  - Thyroid disorder (y/n)
  - Asthma (y/n)
  - Heart disease (y/n)

- Psychiatric disorders (y/n)
  - Inheritable diseases (if yes, specify)
  - Other concomitant illnesses (y/n)
- Concomitant medication (section [8.3.4](#))
- Diabetes mellitus history:
  - Type of DM (T1DM or T2DM)
  - Date of diagnosis of diabetes. If no specific date is available, an approximate date should be entered
  - Date of diagnosis of diabetic complications, if any (according to standard procedure). If no specific date is available, an approximate date should be entered.
    - Retinopathy
    - Neuropathy
    - Nephropathy
    - Macroangiopathy (including peripheral vascular disease) (y/n)
    - Acute myocardial infarction (y/n)
    - Unstable angina (y/n)
    - Heart failure (y/n)
- Current insulin or other injectable antidiabetic treatment:
  - Duration of treatment with insulin, OADs and/or other injectable antidiabetic drugs
  - Start date of current treatment with insulin, OADs and/or other injectable antidiabetic drugs. If no specific date is available, an approximate date should be entered
  - Type, name and dose of current insulin, OADs and/or other injectable antidiabetic drugs

### **8.3.4 Concomitant illnesses and medication**

#### **Concomitant illness**

Any illness that is present at the start of the study (i.e. at the baseline visit) including any pre-planned procedures/surgeries, and any intermittent illness that may not be present at the time of this visit.

For each concomitant illness, date of onset should be recorded. If no specific date is available, an approximate date should be entered.

#### **Concomitant medication**

Details of all concomitant illnesses must be recorded at the baseline visit. Details of all concomitant medication that is expected to continue during pregnancy must be recorded at the baseline visit.

Any changes in concomitant medication up to or equal to 16 weeks must be recorded.

The information collected for each concomitant medication includes start date, stop date or continuing, and indication.

Furthermore information regarding concomitant medication will be collected in the following cases:

- During pregnancy and delivery in case of ADRs, SAEs, major hypoglycaemic episodes and pre-eclampsia
- For the infants in case of ADRs and SAEs
- For both the mother and the infant in case the infant is experiencing an ADR or a SAE and is lactating

### **8.3.5 Maternal anthropometric measurements**

Height (without shoes) will be measured at the baseline visit. Height is measured in metres (m) and recorded with 2 decimals.

Body weight will be measured at the baseline visit and every study visit until delivery. Body weight is measured without shoes, wearing light clothing. Body weight will be recorded in kilograms (kg) with one decimal.

Body mass index (BMI; kg/m^2) will be calculated as weight (kg) divided by height (m) squared in the eCRF.

### **8.3.6 Vital signs**

At each visit the diastolic and systolic blood pressure and pulse will be measured according to standard procedures.

### **8.3.7 Current pregnancy**

The following information will be recorded at the baseline visit:

- Age at conception
- Date of first day of last menstrual period
- GW based on ultra sound scan
- Folic acid taken before and during first trimester (y/n)

### **8.3.8 Major hypoglycaemic events**

Major hypoglycaemia is defined as a hypoglycaemic episode where the patient is not able to treat him/herself and where oral carbohydrates, glucagon or intravenous glucose has to be administered to the patient by another person because of severe central nervous system dysfunction.

The woman will be asked at any visit/contact whether she has experienced any major hypoglycaemic events since last study visit/contact (y/n and if yes how many). These events should be reported according to section [9](#).

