### **KEY SECONDARY ENDPOINTS:**

#### **Maternal endpoints**

- Incidence of major hypoglycaemia during pregnancy
- Proportion of pregnancies complicated by pre-eclampsia during pregnancy

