## 2 Flow chart

Flow chart of visits and standard routine procedures.

Visit	Baseline visit	Standard routine visits	Delivery visit	Follow-up of the infant(s)	Follow-up of the infant(s)
Time of visit	≤ 16 weeks pregnant	Any time during pregnancy	Delivery	1 month after delivery	1 year after delivery
Visit window				+ 1 month	+ 4 months
Informed consent	x				
Incl. /excl. criteria	x				
Demographics	x				
Obstetric history	x				
Maternal medical history	x				
Maternal diabetes history	x				
Current antidiabetic treatment	x	x	x		
Concomitant illness	x				
Concomitant medication	x	x	x		
Height 	x		x	x	x
Weight 	x	x	x	x	x
Vital signs	x	x			
Current pregnancy information	x				
HbA 1c	x 	x	x		
Major hypoglycaemia		x	x		

Pre-eclampsia		x	x		
ADRs and SAEs 		x	x	x	x
Delivery and complications			x		
Pregnancy outcome			x		
Neonatal assessments			x		
Foetal assessments 			x		
Neonatal death				x	
Congenital malformations not detected at delivery				x	
Lactation				x	x
Diabetes					x
Changes of major congenital malformations					x

1. Height and weight of the mother during pregnancy and of the infant(s) at delivery, 1 month and 1 year follow-up
2. HbA1c measured ≤ 16 weeks prior to baseline visit is acceptable as baseline visit data (see section [8.1.1](#))
3. Relevant ADR's and SAE's according to protocol section [9](#)
4. Foetal assessments in case of early termination of pregnancy, perinatal and neonatal death
5. Preferably data from one standard routine visit per month should be entered into the eCRF irrespectively of the number of visits performed

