#### 4.1.2 Secondary objective

##### *Maternal*

Comparison of the following adverse events and abnormal metabolic control in pregnant women treated with Levemir® to pregnant women treated with other basal insulin regimens:

- Incidence of major hypoglycaemic events during the pregnancy period
- Development of pre-eclampsia during pregnancy
- Metabolic control measured as HbA1c during pregnancy

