### **4.2.2 Secondary endpoints**

#### **4.2.2.1 Maternal endpoints**

- Incidence of major hypoglycaemia during pregnancy
- Proportion of pregnancies where the woman experiences at least one major hypoglycaemic event during pregnancy
- Proportion of pregnancies complicated by pre-eclampsia during pregnancy
- HbA1c level assessed as close as possible to conception, end of first trimester, end of second trimester, and at delivery.

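### The major hypoglycaemia endpoints are defined over the whole pregnancy, but the protocol provides for recording events only after the baseline visit

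*Protocol*

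**What the plan says.** **Endpoint.** The Section 1 summary and Section 4.1.2 give the maternal objective as "Incidence of major hypoglycaemic events during the pregnancy period". The summary lists the incidence as a key secondary endpoint. Section 4.2.2.1 repeats it and adds a second endpoint that is not on the key list: "Proportion of pregnancies where the woman experiences at least one major hypoglycaemic event during pregnancy". None of these is limited to time after enrolment.

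**Collection.**
- Section 2, flow chart: the major hypoglycaemia row is marked at standard routine visits and at delivery, and is empty at baseline. The row for adverse drug reactions and serious adverse events is empty there too.
- Section 8.1.1 (baseline list) and Section 8.3.3 (medical and diabetes history): no hypoglycaemia item.
- Section 8.1.2 covers all visits after baseline and asks for "Major hypoglycaemic events since last visit". The delivery list in Section 8.1.3.1 looks back over the same interval.
- Section 8.3.8: "The woman will be asked at any visit/contact whether she has experienced any major hypoglycaemic events since last study visit/contact".

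**Entry.** Section 8.1.1 intends baseline to take place as soon as the pregnancy is discovered. Section 6.3 sets the ceiling: "Women who have been pregnant for more than 16 weeks at baseline visit will be excluded from the study".

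**Analysis.** Under Section 14.4 the incidence is computed in each group. Proportions are compared with Fisher's exact test and also by crude and adjusted logistic regression. Gestational age at entry and exact follow-up time are to be taken into account where relevant. No method is given, and the sentence does not name this endpoint.

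**The concern.** The endpoint covers one period and the data another. A site that follows the protocol exactly will record a woman whose only major events came before her baseline visit as having had none. What is measured is hypoglycaemia from enrolment to delivery, but it would be reported as hypoglycaemia in pregnancy.

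Two consequences follow. The absolute level in each group is understated. The length of the observed window also varies with the week of entry, so the result depends partly on how early women enrol. If entry timing were related to treatment, part of that dependence would pass into the comparison.

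The same variable is used again. Section 14.4 names major hypoglycaemic events during pregnancy as an adjustment factor in the logistic model for the primary endpoint, so the gap carries over to that covariate.

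**Working it through.** The protocol states no figure on this point, so there is none to reproduce. The check has two parts.

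**1. Endpoint wording against collection**

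| Place | Period covered |
|---|---|
| Sections 1, 4.1.2 and 4.2.2.1 (objective and endpoints) | Whole pregnancy |
| Section 2, flow chart | Routine and delivery visits; baseline empty |
| Sections 8.1.1 and 8.3.3 | No item |
| Sections 8.1.2 and 8.1.3.1 | Since the last visit |
| Section 8.3.8 | Since the last study visit or contact |
| Sections 8.2 and 9.1 (general safety question) | Since the last visit or contact |

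No row reaches back from baseline to conception.

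**2. Size of the gap (illustration)**

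Assumptions, not in the protocol: risk runs from gestational week 2 (conception) to week 38 (delivery), which is 36 weeks. The entry weeks are examples. Week 16 is the ceiling in Section 6.3.

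Unobserved share = (entry week − 2) / (38 − 2):
- Week 6: 4/36 = 11%
- Week 10: 8/36 = 22%
- Week 16: 14/36 = 39%

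Effect on the proportion with at least one event. Let P be the true proportion over the 36 weeks. With a constant hazard, observed proportion = 1 − (1 − P)^((38 − entry week)/36). Section 3.1 cites a proportion as high as 71%, used here as an upper example; 30% is an assumed lower one.

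| Entry week | Exponent | P = 71% | P = 30% |
|---|---|---|---|
| 6 | 32/36 | 67% | 27% |
| 10 | 28/36 | 62% | 24% |
| 16 | 22/36 | 53% | 20% |

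Does dividing by follow-up time solve it? With a constant hazard it does, because the rate per observed week is the same whatever the entry week. Suppose instead that the hazard before week 16 is three times the later hazard h (assumption). With P = 71%, the cumulative hazard is −ln(0.29) = 1.238. It equals h × (3 × 14 + 22) = 64h, so h = 0.0193 per week. The observed rates are then:
- Entry at week 6: (3 × 10 + 22)h / 32 = 52h/32 = 0.031 per week
- Entry at week 16: 22h/22 = 0.019 per week
- Whole period: 64h/36 = 0.034 per week

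Person-time therefore removes the dependence on entry week only when the rate is flat over gestation.

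**The case against.** **Section 8.3.8 speaks of any visit or contact, and baseline is a visit.** This is a fair reading of the words, but the question looks back to the last study visit or contact and at baseline there is none. The flow chart and Section 8.1.1 do not provide for it either. The accurate statement is that the protocol makes no provision at baseline. It does not forbid asking.

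**Week 16 is a ceiling.** This stands. Baseline is meant to follow discovery of the pregnancy, and only the weeks before each woman's own baseline are missing. A woman enrolled at week 6 is observed from week 6 onward, so it would be wrong to say that early pregnancy is lost altogether.

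**Section 14.4 takes entry age and follow-up time into account.** This stands in part. It allows person-time to be handled correctly, and the adjusted logistic models could include gestational age at entry, which would reduce any imbalance between groups. It cannot recover events that were not recorded, and the Fisher comparison of the proportion uses no follow-up time.

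**A spurious treatment difference.** A reader might infer that the comparison is biased, for instance that mean entry at week 8 in one group and week 11 in the other gives 30 against 27 observed weeks and about 10% fewer events (27/30 = 0.90). The documents do not support this as a finding. They give no entry weeks by group. Section 5.4 requires all of a clinic's pregnancies to be enrolled whatever the regimen, and Section 5.2 describes closely similar procedures across sites. At a constant rate the 10% difference in counts also disappears once events are divided by follow-up time.

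**The SAP may settle it.** The SAP can fix the denominator and the method. It cannot supply data that the visit schedule does not ask for.

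**Conclusion.** The mismatch between endpoint and data collection is in the text and does not depend on any assumption. Both endpoints would understate major hypoglycaemia in pregnancy, and the window they observe depends on gestational week at entry. The incidence is a key secondary endpoint; the proportion is an ordinary secondary one.

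The size is not known. The shares of 11%, 22% and 39% rest on an assumed risk period of weeks 2 to 38 and on example entry weeks, and the largest applies only at the entry ceiling. The observed proportions rest further on a constant hazard and on the chosen true risk. Bias between the groups is possible but neither shown nor quantifiable from the protocol. The point is mainly one of definition and labelling, and it is worth correcting because the correction is cheap.

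**What to change.** Restate both endpoints in Section 4.2.2.1, the objective in Section 4.1.2 and the matching lines of the summary as running from the baseline visit to delivery or pregnancy termination. Compute the incidence per unit of time from baseline. Account for gestational age at entry when comparing groups: treat it as delayed entry for the incidence and adjust for it in the model for the proportion. Label the covariate in the primary logistic model in the same way. The cost is a rewording and a defined denominator, with no new data. The price is that the endpoints no longer claim to describe the whole pregnancy.

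Optionally, for women still to be enrolled, add a baseline item for the number and dates of major hypoglycaemic events since conception, dated from the last menstrual period and ultrasound data already recorded under Section 8.3.7. Counting from the last menstrual period itself would add about two weeks before conception. Report these events separately, as a supportive whole-pregnancy analysis. This version is dated September 2017 and the first visit was planned for Q3 2013, with a planned recruitment period of 5 years, so folding a recalled item into the main endpoint now would give it two definitions depending on enrolment date. The cost is one eCRF item and recall over at most about 14 weeks (16 − 2).
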